We aim to conduct a single-center randomized controlled trial to measure the impact of physical activity through virtual reality video games on the motor and cognitive performance of youth with MS. Through such a home-exercise program coupled with patient online behavior counseling, we hypothesize that we can significantly impact subjective and objective measures of disease disability in this MS age population.

Objectives

Primary objective: to assess the impact of a virtual reality video (VR) game exercise program on **objective cognitive assessments in youth with MS** (measures outlined below). The **null hypothesis** for this study is that there is no difference in the **Brief Cognitive Assessment for MS** in cognitive disability of youth with MS between those enrolled in a 6-month VR active video game program and those with routine follow-up care. The alternative hypothesis is that there is a difference in measures of cognitive disability between the two groups (two-sided hypothesis).

Secondary objectives:

- To determine the impact of VR physical activity on subjective measures of cognitive, physical and psychosocial disability in youth with MS
- To determine the impact of VR physical activity on the 6-Minute Walk Test (6MWT).

- To determine the number of clinical relapses and new T2 MRI lesions (brain)
- To determine the **safety** of implementing a VR active video game program at home
- To evaluate the effect of VR exercise programs on overall behavior towards physical activity and health promotion in youth through self-report questionnaires

Study Design

- **Single-center, single blinded, randomized controlled trial** comparing a 6-month VR active video game intervention with standard management of physical activity in youth with MS.
- Each participant will be randomly allocated to either the intervention group or the control group for a **period of 6-months** with pre- and post- assessments performed at onset, 3 months, 6 months and 12 months follow-up.
- The study will be conducted over one year with 6 months of intervention. Each group will include 12 subjects (**total subjects = 24**).
- The Microsoft VR active game program will consist of 3 weekly sessions of 45 minutes each combining 3 different types of exercise (cardiovascular and strength with 'Box VR', flexibility with 'Beat Saber', coordination with 'The Climb').

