- To assess the impact of the VR exercise program, a series of subjective and objective assessments will be performed prior to onset, at 3 months, upon completion at 6 months and at 12 months follow-up. These assessments are detailed in the section 'Study procedures' below.
- **Assessment of safety** will be conducted throughout the intervention and will consist of self-reported incidents that occur during the exercise sessions, including falls or physical injuries. These events will be recorded at 1 month, 3 months and 6 months from onset by the investigators.
- **Assessment of adherence** to the program will be documented throughout the study via anonymized exercise logs provided by Microsoft that will monitor participation and overall performance for each game. Microsoft will also provide customer service for any technical difficulties with the VR headsets provided.
- **Personal sessions** with each participant in the intervention group will be conducted via phone calls to educate them on the importance of exercise and assess for any difficulties to adhere to sessions. They will take place at 1 month, 3 months and 6 months. Furthermore, a survey questionnaire will be given to all participants enrolled in the intervention group at the 6-month follow-up time to determine the degree of incorporation of physical activity into their daily life following completion of the study.

Study Population

- Inclusion criteria: (1) **age between 15-25 years**, (2) **confirmed diagnoses of Pediatric-Onset MS (<18 years)** according to the 2017 revised McDonald criteria (relapsing-remitting), (3) **Expanded Disability Status Scale (EDSS) ≤ 5.0**, (4) **relapse free for the past 30 days**, (5) **no contraindications to physical activity**, including pregnancy (6) no history of visual provoked seizures and (7) participant and parent (if between 15 and 18 years of age) **written informed consent**.
- The participants will be recruited through the neurology clinic in Houston using phone, email or postal communications. People who are interested in taking part will be contacted by the research team via phone or email and explained the study in detail. If the selection criteria are met, informed consent forms and participant information leaflets will be sent via post or email, or obtained during a routine clinic visit.

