- The subjective assessments will be mailed to the participants or given when seen in clinic. Study staff will perform the 6MWT at the time of a routine clinic visit and will require no additional costs.
- The three cognitive assessments per subject will be carried out by a qualified neuropsychologist or neurologist and will be performed at the time of a routine clinic visit.

Data and Safety Monitoring

- During the course of study participation, subjects might experience an adverse event related to the physical activity or to their underlying MS. These events might include falls, musculoskeletal injuries, neurological symptoms suggestive of a clinical relapse, or any other physical or psychological cause of distress. These events will be documented by participant self-reports and contacting study personnel. They will be graded from 1 to 3 according to their degree of severity with 1 = mild, no interference with daily activities, 2 = moderate, some interference with daily activities and 3 = severe, significant interference with daily activities and requiring medical intervention.
- The research team will perform a **periodic review of adverse events** recorded once every 2 months as well as an assessment of adherence to the exercise programs and any other concerns raised by the research team or the participants.
- In the event of a clinical relapse or worsening of a participant's neurological symptoms, the research team will promptly inform the MS specialist in charge of that participant's care. Subject's participation in the intervention group will cease.

Statistics

- Statistical analysis will be performed using the software program **Stata version 15**.
- Descriptive numerical or graphical summaries will be used for demographic and clinical characteristics of the sample population at baseline. Independent samples t-tests and chi-square tests will be done to assess differences between intervention and control groups on pre-trial and post-trial assessments. Only participants who completed the 6-month exercise program will be included in the analysis of the intervention group but missing data will be noted. Paired sample t-tests and chi-square tests will be conducted to determine differences in pre-trial and post-trial assessments within each group. If data reveals a skewed distribution, Kruskall Wallis tests will be used for continuous variables. All tests will be conducted using an alpha = 0.05 level of statistical significance.

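### In the protocol text, a severe fall, injury or episode of distress brings no prompt study response, because prompt notice and stopping are tied only to relapse or neurological worsening

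*Combined protocol and SAP*

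**What the plan says.** The secondary objectives include the safety "of implementing a VR active video game program at home".

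The Data and Safety Monitoring section anticipates falls, injuries, relapse-like neurological symptoms and other physical or psychological distress. On capture it says: "These events will be documented by participant self-reports and contacting study personnel". Events are graded 1 to 3, and the top grade is "3 = severe, significant interference with daily activities and requiring medical intervention". The research team's periodic review covers what has been "recorded once every 2 months as well as an assessment of adherence to the exercise programs". Its scope extends further, to "any other concerns raised by the research team or the participants".

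The last bullet of that section holds the only prompt step: "In the event of a clinical relapse or worsening of a participant's neurological symptoms, the research team will promptly inform the MS specialist" responsible for the participant. The next sentence of the same bullet ends the person's part in the intervention.

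Study Design says that safety assessment "will be conducted throughout the intervention and will consist of self-reported incidents that occur during the exercise sessions, including falls or physical injuries", and adds: "These events will be recorded at 1 month, 3 months and 6 months from onset by the investigators". Intervention participants also have phone sessions at those three time points, for education and adherence problems. Study Procedures sets a minimum of three 45-minute VR sessions a week for 6 months. It also provides two education sessions without dates, and the HADS at weeks 1 and 12 and at 6 and 12 months.

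**The concern.** The protocol defines a severity scale but attaches no action to it. What triggers a response is the type of event. Followed as written, a mild relapse leads to prompt notice and the end of VR, while a fall or injury that needed medical care leads to neither. The instruction to play at least three times a week stays in force.

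Participants are 15 to 25 years old, have an EDSS of up to 5.0, and play in a headset at home. Entry requires that physical activity is not contraindicated. A severe injury could create such a contraindication after entry, and the text asks no one to look again. At stake are the safety of the person concerned and how soon the trial's own safety objective learns of the event.

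**Working it through.** The plan gives no figure on this point, so there is none to reproduce. The check sets the safety provisions side by side and reads the intervals off the stated schedule.

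**Step 1. Which events trigger action?** (Data and Safety Monitoring)

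| Event once reported | Prompt notice | Intervention ends | Next stated study step if not prompt |
|---|---|---|---|
| Relapse or neurological worsening, any grade | Yes | Yes | n/a |
| Fall or injury with neurological worsening | Yes, same trigger | Yes, same trigger | n/a |
| Grade 3 fall, injury or distress, no neurological worsening | Not stated | Not stated | 2-monthly review |
| The same at grade 1 or 2 | Not stated | Not stated | 2-monthly review |

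The last two rows are identical, so the grade changes nothing. The gap is confined to the third row.

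**Step 2. Does other text fill the gap?**

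- Recording at months 1, 3 and 6 (Study Design) says when incidents are written down, not what follows.
- The phone and education sessions could bring an event to light, but their stated purpose is education and adherence.
- The HADS measures anxiety and depression, but no score leads to an action.
- Withdrawal of consent (Ethics) is the participant's choice, not a clinical decision.
- The grade 3 definition says that care was needed. It does not say who in the study acts, when, or whether exercise is paused.

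None of these states a prompt step.

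**Step 3. How long can an event wait?**

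- *Reported event.* Reviews are 2 months apart, so the longest wait for a review is 2 months. The start of the cycle is not given; I assume the first review is no later than month 2. A recording or phone contact may come sooner, but no decision is tied to it.
- *Event not volunteered.* Solicited recording is at months 1, 3 and 6. The gaps are 1 − 0 = 1, 3 − 1 = 2 and 6 − 3 = 3 months. The longest wait is 3 months, for an event just after month 3 that no adherence review or education session uncovers.

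Both are upper limits in calendar time. Neither estimates the usual delay or how long anyone would go on playing.

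**The case against.** The other side has several fair points.

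- **Participants can contact staff at any time, and clinicians would probably act sensibly without a written rule.** This stands. What is missing is the stated response, not the chance to report.
- **Consent documents, study schedule and data form are listed as attachments and cannot be seen.** Instructions on injury may be there. This stands, and it limits the point to the protocol text.
- **Waiting times do not measure a missing response to a known event.** This stands. An average can be computed: for solicited recordings alone, with event times uniform over 6 months, it is (1² + 2² + 3²)/(2 × 6) = 14/12 = 1.17 months. It rests on an assumption the documents do not support and says nothing about what happens once an event is known. Only the upper limits are used here.
- **Notice to an MS specialist suits a relapse better than a fracture, and grade 3 already implies medical care.** This stands in part. The doctor who treats a fracture need not know about the VR programme, so someone connected with the study still has to decide whether it continues.
- **Wider notice could unblind an assessor.** This is a real risk. An MS specialist does the walk test and may do the cognitive tests, and assessors are meant to be blinded. The present relapse trigger carries the same risk without any blinding condition, and blinding is no reason to withhold notice of a severe injury from the treating doctor.

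A reader might infer that severely injured participants would keep playing for months, that safety events would be lost, or that the cognitive result would be biased. The documents do not support these readings. Self-report is open throughout, an event that is not volunteered would mostly be recorded late rather than missed, and nothing in the gap bears directly on the primary cognitive comparison.

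**Conclusion.** The point holds for the protocol text. Prompt notice and stopping depend on relapse or neurological worsening alone, so a reported non-neurological grade 3 event has no stated study action before the next 2-monthly review. After month 3, an event that is not volunteered may not be solicited until month 6.

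The limits are 2 months and 3 months respectively. They rest on the stated schedule, on the assumed first review by month 2, and, for the second, on no other contact revealing the event. The number of people affected cannot be estimated: no event rate is given, and the intervention group has 12 participants.

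This is more than a missing detail, because a rule exists and its trigger is too narrow for the events the same section anticipates. It remains a cheap improvement of modest severity.

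**What to change.** In Data and Safety Monitoring, widen the existing trigger:

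1. Grade every event when it is reported. Notify any grade 3 event promptly, within a time the investigators set, to an investigator and to the treating MS specialist, without exception.
2. Hold VR sessions until a clinician records a decision to continue, pause or stop. The clinical criteria are for the investigators to choose.
3. If the notice unblinds that participant's assessor, have another available blinded assessor do the later assessments where possible. The protocol already allows a neuropsychologist or an MS specialist for the cognitive tests. Otherwise record the unblinding. Notice is never withheld.

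Optionally, add an adverse-event line to the sport-activity records that participants in both groups keep. Do not rely on the exercise logs that Study Design describes as anonymized and supplied by Microsoft, since they may not identify the person. Collecting the records between months 3 and 6 would be a small new task, because no study visit is scheduled then.

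The cost is a few sentences, some paused sessions and slightly more form handling. Because the Statistics section analyses only completers in the intervention group, the protocol should also say whether someone with a held period counts as having completed.

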- Qualitative analysis will be performed through a survey questionnaire collected at the time of the 6-month follow-up, to determine participants' experience and longer term perspectives with regards to the integration of physical activity in the management of their disease.
- The selection of subjects to be included in the analyses will comprise all of those randomized to the control group and all of those randomized to the intervention group who completed the 12-week

exercise program. Dropouts at all stages (enrollment, randomization, intervention, 6-month follow-up) will be recorded.

Ethics

- IRB approval will be sought from CPHS prior to initiation of this study.
- Prior to enrollment in the study, all subjects and parents will be explained all parts of the research in a detailed manner by one of the study investigators. This will be conducted in a quiet environment either at the UT Clinic or by phone. Participants will be given the opportunity to ask questions during the consent process and at any time for the duration of the study. There will be no time limit to obtaining patient consent. Subjects will also be allowed to withdraw their consent at any time by contacting one of the study's investigators.

Data handling and record keeping

- Upon obtaining informed consent from each participant and all selection criteria met, study personnel will access demographic characteristics and all clinical data relevant to MS. This will include past and current disease-modifying therapies (DMTs), symptomatic treatments, EDSS score at enrollment time, burden of disease on MR imagery as well as quantitative information on the degree of physical activity at the time of enrollment.
- All information obtained during the study will be stored on a password-access database that can only be viewed and modified by the PI and co-investigators.
- All subjects enrolled in the study will be attributed a coded number and all personnel information will be de-identified upon collection. The subject codes will be maintained by study staff within the secure database only accessible by study staff and on UT Health-supported servers approved for storing PHI.

Quality control and assurance

- Staff investigators will conduct the subjective and objective assessments. All assessors will be blinded to subject group allocation and subjects will be instructed not to inform them of their allocated group.

Publication Plan

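### A relapse removes a VR participant from the analysis but not a control, so known VR relapses count as zero up to programme completion

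*Combined protocol and SAP*

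**What the plan says.** Four statements in the combined protocol and SAP bear on this.

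- **Objectives (secondary).** The number of clinical relapses, with new brain T2 lesions, is a stated objective.
- **Data and Safety Monitoring.** A relapse or neurological worsening is reported to the treating MS specialist, and the consequence for the VR arm is then given: "Subject's participation in the intervention group will cease". There is no provision for restarting and no matching rule for controls. The same section lists "neurological symptoms suggestive of a clinical relapse" among the adverse events to be documented, so these events are recorded.
- **Statistics, second bullet.** "Only participants who completed the 6-month exercise program will be included in the analysis of the intervention group", with missing data to be noted.
- **Statistics, last bullet.** The analyses take in "all of those randomized to the control group and all of those randomized to the intervention group who completed the 12-week" programme. Dropouts are to be recorded.

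The two Statistics sentences disagree on what completion means (6 months or 12 weeks). They agree on the asymmetry: completion is required in the VR arm and not in the control arm. No intention-to-treat analysis, safety set or sensitivity analysis is given, and the relapse count is not exempted from the selection rule.

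**The concern.** Each rule can be read as reasonable alone. Stopping exercise after a relapse is a sensible precaution. Together, the two rules make a trial outcome decide who is analysed, in one arm only.

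Two comparisons are affected. The relapse comparison loses every known VR relapse before the completion point and keeps every control relapse, so VR would look protective even if it did nothing. If VR raised the relapse rate, the adverse event log would show it but the between-arm comparison would not. For BICAMS, the 6-minute walk and the questionnaires, people who have recently relapsed remain only among controls, which favours VR.

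There is also a gap in follow-up. The plan does not say that a stopped participant keeps the 6- and 12-month assessments. If those visits lapse, a corrected analysis set would have no scores to use.

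**Working it through.** **The zero follows from the text.** A VR participant relapses before the completion point and the team learns of it. Participation in the VR arm ends, so the programme is not completed and the participant is not analysed. A control with the same relapse meets no stopping rule and no completion condition, and is analysed. No relapse rate is needed for this step.

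**Inputs for size.** From the documents: 12 participants per arm; 6 months of intervention, then 6 months of follow-up; two-sided alpha of 0.05; t-tests and chi-square tests between groups. The plan states no power, standard deviation, relapse rate or dropout rate, so it has no figure to reproduce. Assumed: Poisson relapses at the same annualised relapse rate (ARR) in both arms, from 0.3 to 1.0; completion point t = 0.5 years (6 months) or 12/52 = 0.231 years (12 weeks).

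**Counts up to the completion point, no true VR effect**

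| Quantity | Formula | 6-month wording | 12-week wording |
|---|---|---|---|
| Expected control relapses | 12 × ARR × t | 1.8 to 6.0 | 0.83 to 2.77 |
| VR relapses analysed | none | 0 | 0 |
| VR participants removed (of 12) | 12 × (1 − exp(−ARR × t)) | 1.67 to 4.72 | 0.80 to 2.47 |
| Chance that at least one is removed | 1 − exp(−12 × ARR × t) | 0.835 to 0.998 | 0.564 to 0.937 |

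**Relapses to month 12.** Controls have ARR × 1 per analysed person, which is 0.30 to 1.00. VR completers contribute only the time after completion, ARR × (1 − t), which is 0.15 to 0.50 under the 6-month wording. The apparent rate ratio is 1 − t: 0.50 under the 6-month wording and 0.77 under the 12-week wording, at any ARR, when the true ratio is 1.

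**If VR doubled the rate in months 0 to 6.** Expected VR relapses would be 12 × 2 × ARR × 0.5 = 3.6 to 12.0 if everyone were counted, and still 0 among 6-month completers.

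**Chi-square test on any relapse in months 0 to 6, no true effect.** Exact enumeration over both arms, without continuity correction:

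| Assumed ARR | 6-month VR completers v all controls | All 24 by allocated arm |
|---|---|---|
| 0.2 | 2.0% | 1.3% |
| 0.3 | 6.1% | 2.7% |
| 0.4 | 11.7% | 3.6% |
| 0.6 | 24.3% | 4.5% |
| 1.0 | 48.1% | 5.9% |

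**Cognitive scores.** Assume that any relapse in months 0 to 6 lowers the month-6 score by 0.3 to 0.5 SD. The bias toward VR is that effect times the difference between arms in the proportion who relapsed.

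- 6-month wording: (1 − exp(−0.5 × ARR)) × effect = 0.139 × 0.3 = 0.04 SD, up to 0.393 × 0.5 = 0.20 SD.
- 12-week wording: VR participants who relapse after week 12 stay in, and 0.5 − 0.231 = 0.269 years remain. The bias is [(1 − exp(−0.5 × ARR)) − (1 − exp(−0.269 × ARR))] × effect = (0.139 − 0.078) × 0.3 = 0.02 SD, up to (0.393 − 0.236) × 0.5 = 0.08 SD.

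For scale, a two-sample t-test with 80% power detects 1.20 SD with 12 v 12, 1.26 SD with 10 v 12 and 1.41 SD with 7 v 12.

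**The case against.** The strongest reply is that the plan never specifies a relapse comparison. The objective speaks of a number of relapses, with no arm contrast, window or test. The between-group tests are attached to pre- and post-trial assessments, and relapse is not among the assessments listed under Study Procedures. A descriptive count could come from the adverse event record, which covers both arms. That reading is possible, but the last Statistics bullet sets the population for the analyses without exception, and a plan followed as written applies it to relapses too.

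Other points stand as limits:

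- The zero covers relapses that reach the team and trigger the stop. An unreported relapse could remain, and because completion is not defined, one at the very end of the programme could be classed either way.
- At an ARR of 0.3 the chi-square error rate is 6.1%, close to nominal. Serious error in a formal test needs higher rates, although the lopsided counts do not.
- The cognitive bias is small beside the detectable difference, and smaller still under the 12-week wording.
- Loss of follow-up is not shown. Questionnaires go to all participants, and the stopping sentence ends only participation in the VR arm. The plan is silent here rather than wrong.

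It is also fair to say that this is one consequence of the general completers-against-all-controls rule, and that correcting that rule removes most of it. It merits its own point because here a protocol rule turns an outcome event into an exclusion, and because the follow-up of stopped participants needs its own sentence.

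Recording dropouts and noting missing data does not answer the concern, since neither returns anyone to the comparison.

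**Conclusion.** The concern holds and the plan is wrong as written; this must be fixed. Under either completion wording, known VR relapses before the completion point are removed from the analysis and control relapses are kept. That result and its direction need no assumption beyond applying the stated selection rule to the relapse count.

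The size depends on the assumed ARR of 0.3 to 1.0, except for the apparent rate ratios of 0.50 and 0.77, which require only a constant and equal rate. The main harm is to the relapse comparison, which could hide an increase in relapses during the programme. The effect on cognition is real in direction but modest: 0.02 to 0.20 SD across both wordings, resting on an assumed relapse effect. The stopping trigger also includes neurological worsening without a relapse, so the selection is somewhat wider than these figures show.

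**What to change.** Keep the safety stop and change three things.

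1. **Data and Safety Monitoring.** Add: *Stopping the VR sessions does not end study follow-up. The participant stays in the allocated arm and keeps the scheduled 6- and 12-month assessments.*
2. **Statistics, both bullets.** Replace the completer restrictions with analysis of all randomized participants by allocated arm. A completer analysis may stay if labelled supplementary, with one definition of completion.
3. **Relapse outcome.** Count relapses from randomization to month 12 in all 24 participants by allocated arm, including the relapse that triggered the stop, and report them per person-time.

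The cost is a few sentences in an amendment. The assessments already take place at routine clinic visits and relapses are already documented as adverse events, so no visits or staff are added. The one drawback is that some VR-arm scores will come from people no longer using VR.
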